6.12.2 Adverse events and Serious Adverse events

All AE will be coded according to MeDDRA version 25.1.

Concerning Adverse Events (AE) a summary of treatment-emergent adverse events (TEAE), including the total number of events reported, the number and percentage of patients reporting at least one adverse event, the number and percentage of IMP-related adverse events, the number and percentage of patients withdrawing prematurely due to an adverse event, the number and percentage of patients with at least one serious adverse event (SAE), the number of non-fatal serious adverse events and the number and percentage of deaths, will be presented by treatment.

A further tabulation of TEAEs by SOC and PT, and TEAEs by SOC and PT broken down by relationship to study drug will be presented. Relationship to study drug is categorized as none, unlikely, possible, probable and highly probable as recorded on the CRF. A summary of TEAEs reported by SOC and PT, broken down by severity (mild, moderate, severe, life threatening), will also be provided. In addition IMP related adverse events, deaths and non-fatal serious adverse events will be tabulated.

A summary of TEAEs leading to premature withdrawal will be provided, grouped by body

	STATISTICAL ANALYSIS PLAN	FSTAT.01.03
Study Code: HEM-HEM-01-17		Sealantium Medical Ltd.

system and preferred term.

All tabulations by SOC and PT will be replicated for all serious TEAEs.

All adverse events recorded on the CRF will be listed.

6.12.3 Thrombotic and TBS related Bleeding Events

Summary statistics of thrombotic events and TBS related bleeding events/ complications will be presented separately by SOC and PT according to adverse event table layout by treatment.

6.12.4 Post-operative Adhesions - MRI assessment

MRI will be evaluated at screening visit and after 180 days after surgery (visit 9). Moreover, additional MRIs will be performed if the Investigator identifies signs and symptoms of unanticipated or unexpected persistent inflammatory response that can cause in the post-surgery risks for intra-abdominal adhesion or bowel obstruction.

Number and percentage of patients showing signs and symptoms and number of patients having shown signs at least once over the study period will be summarized by visit.

Specification of signs and symptoms are documented in the adverse event page and analyzed in this section.

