11.1.9. Visit 9 (Day 180±14 after surgery) – Follow up Visit #4

The following information will be recorded at the clinical follow-up visit approximately six months following surgery:

- Physical examination and documentation of any changes in medical history.
- Vital signs (blood pressure, heart rate, temperature, respiratory rate).
- Blood hematology and biochemistry (see Schedule of Assessments for the list of tests).
- Measurement of coagulation parameters (PT, PTT, INR).
- Urine analysis (see Schedule of Assessment for the list of tests).
- Testing of antibodies levels (against Human Fibrinogen and Human Thrombin).
- MRI assessment of the intervention site (mainly to exclude post-operative adhesions). This assessment can be done earlier in patients reporting abdominal symptomatology suspect for intra-abdominal adhesions or intestinal obstruction (ref. 12).
- Adverse events (in particular related to post-operative adhesions, systemic inflammation, bleeding / thrombotic and transfusion-related complications).
- Transfusion requirements.
- Concomitant medications.

All patients can request or be requested to be evaluated in an additional visit (i.e., in case of suspected adverse events). In such case will be examined as needed indicated at Section 13.5.

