13.1. Adverse Event (AE)

An adverse event (AE) is defined as any untoward medical occurrence in a patient or clinical trial patient administered a medicinal product and which does not necessarily have a causal relationship with the treatment. In the study, any adverse event occurring after the clinical trial patient has signed the study Informed Consent should be recorded on the eCRF and reported as an AE. An adverse event can therefore be any unfavorable and unintended sign (including an abnormal laboratory finding), symptom, or disease temporally associated with the use of an investigational medicinal product, whether or not considered related to the investigational medicinal product. A new condition or the worsening of a pre-existing condition will be considered an AE. Stable chronic conditions such as arthritis that is present prior to study entry and do not worsen during

the study will not be considered AE. Medical conditions/diseases present before starting study are only considered adverse events if they worsen after starting study treatment.

Abnormal results of diagnostic procedures, including abnormal laboratory findings, will be considered an AE if it:

- it is associated with significant clinical signs or symptoms;
- requires therapy.

Post-operative adhesions will be considered adverse events in this study. A MRI assessment will be performed at Visit 1 (Screening) and at Visit 7 (6 months post-surgery) for detection of intra-abdominal adhesions, or earlier in patients reporting abdominal symptomatology suspect for intra-abdominal adhesions or intestinal obstruction (ref. 12).

Systemic inflammation will be evaluated by the investigator, based on the following assessments:

- Body temperature, heart rate, respiratory rate, white blood cell count, CRP

The intensity or severity of the AE will be characterized as:

- Mild: AE which is easily tolerated.
- Moderate: AE sufficiently discomforting to interfere with daily activity.
- Severe: AE which prevents normal daily activities.

The relationship of an AE to the study product must be assessed by the Investigators using the following criteria and definitions:

Unrelated	This category applies to those adverse events which, after careful consideration, are clearly due to extraneous causes (disease, environment, etc.)	

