3.3 Study Endpoints

3.3.1 Primary Endpoint

The primary endpoint of the study consists of multiple safety variables as a composite marker for the safety. Variables of the composite marker were assessed during all study periods: from randomization to end of follow-up. It includes evaluation of treatment emergent adverse events (TEAEs), particularly TEAEs related to bleeding at TBS, thrombotic events, transfusion-related complications, post-operative adhesions (MRI assessment). It also includes evaluation of vital signs, physical examination, urine analysis, blood/coagulation parameters profiles, antibodies against fibrinogen and thrombin, and signs of systemic inflammation.

Primary endpoint is considered as a composite endpoint, because it includes multiple explanatory variables that support safety and tolerability of study treatment on the efficacy claim.

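### SAP 6.12.4 summarises the MRI-assessed adhesion component of the primary endpoint as a signs-and-symptoms count from the adverse event page, with no MRI adhesion variable, no change from Screening and no scanned-patient denominator.

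*SAP*

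**What the plan says.** **Status of the component.** The primary endpoint in SAP 3.3.1 includes "transfusion-related complications, post-operative adhesions (MRI assessment"), and Protocol 12.1 and 14.8.1 name the same component. SAP 6.12 lists MRI assessment as a safety item of its own, separate from adverse events.

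**Data planned.** The schedules in both documents give every patient an MRI at Screening and at Day 180 (Visit 9). Protocol 11.1.9 gives the purpose of the later scan: "MRI assessment of the intervention site (mainly to exclude post-operative adhesions"). Symptoms may prompt extra or earlier scans.

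**Analysis planned.** SAP 6.12.4 carries adhesions and MRI in its title and restates the timing: "MRI will be evaluated at screening visit and after 180 days after surgery (visit 9"). The statistic it then names is "Number and percentage of patients showing signs and symptoms and number of patients having shown signs at least once over the study period", summarised by visit. On the source it says: "Specification of signs and symptoms are documented in the adverse event page and analyzed in this section".

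**Recording rules.** Protocol 13.1 states: "Post-operative adhesions will be considered adverse events in this study". It continues: "A MRI assessment will be performed at Visit 1 (Screening) and at Visit 7 (6 months post-surgery) for detection of intra-abdominal adhesions" (its Visit 7 is Visit 9 in the schedule). Just before this, the same section says: "Abnormal results of diagnostic procedures, including abnormal laboratory findings, will be considered an AE if it" has significant clinical signs or symptoms, or requires therapy.

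**The concern.** The component is an imaging outcome, measured before and after surgery in everyone. The planned statistic is a clinical count. In the sentence of SAP 6.12.4 that precedes it, signs and symptoms are what prompts an additional MRI, not what an MRI shows. Three items needed to report an imaging outcome are absent from the section: the result variable (adhesion present or absent), the comparison with Screening that makes an adhesion new, and the number of patients scanned.

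At stake is a primary safety comparison for an implanted film. If one product produced more silent adhesions than the other, a table driven by symptoms might not show it, although the scans that could show it are already scheduled.

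**Working it through.** The point is mainly textual, so the passages are set side by side first.

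**1. Can a silent Day 180 adhesion reach the SAP 6.12.4 table?** The table draws on the AE page, so the finding must first be recorded as an AE. Protocol 13.1 gives two answers:

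| Rule in Protocol 13.1 | Silent, untreated adhesion on MRI |
|---|---|
| Post-operative adhesions are AEs (no symptom condition) | Recorded |
| An abnormal diagnostic result is an AE if it has significant signs or symptoms, or needs therapy | Not recorded |

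The section does not say which rule governs. SAP 3.5 refers to three centres, so the rule could be applied in different ways. Even when recorded, an asymptomatic adhesion does not clearly belong in a row labelled signs and symptoms.

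**2. Is a new adhesion separated from an old one?** Protocol 13.1 treats a pre-existing condition as an AE only if it worsens. Applying that to adhesions means comparing the later scan with the Screening scan, and neither document specifies that comparison. SAP 6.12.5.2 and 6.12.6, by contrast, prescribe shift tables from baseline for physical examination and laboratory results.

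**3. What is the denominator?** The Safety Analysis Set is everyone who received at least one dose. A patient who leaves before Day 180 is replaced but stays in that set. On an AE-based count this patient, without a post-operative MRI, has no adhesion entry and looks the same as a patient with a clear scan. SAP 6.5 applies no approach to missing data.

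**4. Early scans.** Protocol 11.1.9 lets the Day 180 assessment be done earlier when symptoms suggest adhesions or obstruction. SAP 6.12.4 speaks of additional MRIs. Neither says whether an early scan replaces the Day 180 scan in a by-visit table.

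**5. Scale.** The documents give no adhesion rate and no precision figure for adhesions. Their one precision figure is for hemostasis (Protocol 14.8.2): 80% of 15, with an exact 95% interval of 52% to 96%. The Clopper-Pearson limits for x out of n are the 2.5% quantile of Beta(x, n−x+1) and the 97.5% quantile of Beta(x+1, n−x). For 12/15 they are 51.9% and 95.7%, which reproduces that figure.

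The same method applied to assumed counts, 15 scanned patients in one arm, 6 with a silent new adhesion and 1 with a symptomatic one:

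- symptomatic cases only: 1/15 = 6.7% (0.2% to 31.9%);
- all new adhesions on MRI: (6+1)/15 = 7/15 = 46.7% (21.3% to 73.4%).

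With the 6 silent cases alone, the two counts would be 0/15 (0% to 21.8%) and 6/15 (16.3% to 67.7%).

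Over a range of assumed values, let p be the MRI adhesion rate and s the symptomatic share. The chance that an arm of 15 shows no case is (1−p·s)^15 for symptomatic cases and (1−p)^15 for MRI cases:

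| p | s | Expected on MRI, 15p | Expected symptomatic, 15ps | P(no symptomatic case) | P(no MRI case) |
|---|---|---|---|---|---|
| 20% | 5% | 3 | 0.15 | 86% | 3.5% |
| 40% | 10% | 6 | 0.6 | 54% | below 0.1% |
| 80% | 25% | 12 | 3.0 | 3.5% | below 0.1% |

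These figures describe only the reading in which silent adhesions are left out. For the denominator, if 3 of the 15 had no post-operative MRI, the same 7 cases would be 7/15 = 46.7% of treated patients but 7/(15−3) = 7/12 = 58.3% of scanned patients.

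**The case against.** A reader might infer that a silent adhesion can never enter the tables, that only symptomatic events will be reported, or that SAP 6.12.4 is the only place where the component is analysed. The documents support none of these.

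- Protocol 13.1 makes post-operative adhesions AEs without a symptom condition. Being study-specific, that sentence can fairly be read as overriding the general rule on diagnostic results. A silent adhesion would then reach the AE page, the AE tables by system organ class and preferred term (SAP 6.12.2), and the listings.
- SAP 6.12 promises that all safety data, MRI included, will be listed and tabulated by arm at each time point. It also plans a medical reviewer to classify safety endpoints before database lock.
- Signs could mean signs on imaging, given the section title.
- Pre-existing adhesions are partly covered by the worsening rule.
- SAP 6.1 takes percentages over non-missing responses, which for an MRI result field would exclude unscanned patients.
- The mock tables, the mock listings and the annotated eCRF are separate documents and may define an MRI field.
- The study is descriptive, with no hypothesis tests and no decision rule tied to an adhesion rate.

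These arguments remove the absolute claims and lower the severity. The gap remains. The AE route rests on choosing one of two conflicting sentences. The general promise in SAP 6.12 names no MRI variable. The worsening rule needs a comparison of scans that is not specified. The non-missing rule does not help with an AE count, because a patient without an AE entry is not a missing response. A definition in the shells would still need to be stated in the SAP.

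**Conclusion.** The point holds as a defect in the definition of a primary safety component. For an outcome assessed by MRI, SAP 6.12.4 names a clinical count from the AE page and defines no MRI adhesion variable, no change from Screening and no denominator of scanned patients. Silent adhesions may be missed or recorded differently between sites. On the AE route, patients without a post-operative MRI would count as adhesion-free.

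The size cannot be estimated from the documents. The contrast of 1/15 with 7/15 rests on assumed counts and on the symptoms-only reading; it shows what could be lost and does not predict a result. If every MRI adhesion is entered as an AE, the AE tables would contain the silent cases, and what remains is the missing comparison with Screening and the missing denominator.

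This should be fixed, with medium confidence, because the mock tables and eCRF could not be checked.

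**What to change.** In SAP 6.12.4:

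- Define the analysis variable as adhesion at the intervention site on MRI, present or absent. A new adhesion is one absent at Screening and present on a post-operative MRI.
- Report new adhesions per arm as n/N, where N is the number of patients with both MRIs evaluable, with an exact 95% confidence interval. State how many treated patients fall outside N.
- Show symptomatic adhesions, asymptomatic adhesions and symptom-triggered MRIs as separate rows.
- State how an early MRI and a missing Day 180 MRI are counted.

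In Protocol 13.1, reconcile the two sentences so that all sites record MRI-detected adhesions in the same way, whether or not there are symptoms.

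The cost is SAP wording, one table shell and a small protocol clarification. The scans are already scheduled. Check first that the eCRF holds the MRI result in a form that can be tabulated, and settle the definitions before database lock.

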6.12.5 Vital Signs and Physical Examination

6.12.5.1 Vital Signs

Vital signs, including systolic (mmHg), diastolic blood pressure (mm Hg), heart rate (beats/min), respiratory rate (breath/min) and body temperature (°C), are measured at Screening, Baseline, Surgery, Post- Surgery, Hospital Discharge and Follow-up (after 30, 60, 120 and 180 days from Surgery). Summary statistics for each of these parameters will be presented by treatment group at each time point.

6.12.5.2 Physical Examination

Physical Examination (Eyes; Ears, Nose and Throat; Head and Neck; Cardiovascular; Lungs; Abdomen; Musculoskeletal; Lymph nodes; Skin; Urogenital System; mental State; Other) is measured at Screening, Baseline, Hospital Discharge and Follow-up (after 30, 60, 120 and 180 days from Surgery). For each body system counts and percentages for the clinically abnormality will be presented by treatment group at each time point. Shift tables will present changes in frequency of normal and abnormal values for each post-baseline value to baseline. Shift tables will differ between body systems.

6.12.6 Clinical Laboratory Data

Results for each parameter at each time point and treatment will be presented as listing, low (L) and high (H) values will be flagged in listings; in the listing will be reported the normal range of each parameter processed, too. The following table will be used for all laboratory parameters:

	STATISTICAL ANALYSIS PLAN	FSTAT.01.03
Study Code: HEM-HEM-01-17		Sealantium Medical Ltd.

1. Summary statistics in terms of number and percentages for categorized parameters will be generated by time point and treatment.
2. In case of continuous measurements descriptive statistics will be presented by time point.
3. Normal, abnormal Not Clinically Significant (NCS) and abnormal Clinically Significant (CS) counts and frequency classifications will be tabulated for all parameters having recorded data about.
4. Shift tables will show changes in frequency of normal, abnormal NCS and abnormal CS values for any post-baseline value compared to Baseline.
5. All continuous parameters will show tables with absolute change from Baseline.

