11.1.2. Visit 2 (Day -1 before Surgery) – Baseline Visit

The following activities will be performed within 24 hours prior to the surgical procedure. Visit 2 will be skipped in case V1 is performed at Day -1.

Eligibility Criteria evaluation. In the event that a patient is not eligible, the reason will be documented on the eCRF and screening log.

- Physical examination and documentation of any changes in medical history from the screening visit.
- Eligibility Criteria verification. In the event that a Patient is not eligible, the reason will be documented on the eCRF and screening log.
- Vital signs (blood pressure, heart rate, temperature, respiratory rate).
- Pregnancy test (β -HCG urine test) for female patients of childbearing potential.
- Blood hematology and biochemistry (see Schedule of Assessments for the list of tests).
- Measurement of coagulation parameters (PT, PTT, INR).
- Urine analysis (see Schedule of Assessment for the list of tests).
- Concomitant medications documentation during 24 hours prior to surgery.

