14.1 Sample Size Determination

The sample size will be of 30 patients completing the study. 15 patients will be included in the experimental treatment arm (Group A) and 15 patients in the active-comparator arm (Group B) to allow an adequate comparison between treatments.

Dropped patients during the course of the study will be replaced.

The sample size of 15 patients per arm is sufficient for planned descriptive analyses and 95% confidence intervals of efficacy.

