14.5 Level of Significance

Hypothesis testing is not specified for this study, rather estimation of efficacy endpoints will be accompanied by 95% exact confidence intervals.

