6 STATISTICAL ANALYSIS METHOD

6.1 General Principles

In general, categorical data will be presented using counts and percentages, whilst

	STATISTICAL ANALYSIS PLAN	FSTAT.01.03
Study Code: HEM-HEM-01-17		Sealantium Medical Ltd.

continuous variables will be presented using the mean, standard deviation, standard error of mean, median, minimum, maximum and number of patients. Minima and maxima will usually be reported to the same level of accuracy as the raw data; means, medians, will be presented to one further decimal place; standard deviations and standard errors will be presented to 2 decimal places more than the raw data. Percentages will be rounded to the nearest integer or with one decimal. In tabulations, denominators for calculation of percentages will be taken as the number of non-missing responses in the specified analysis population and treatment group unless otherwise stated. 95% Clopper-Pearson Confidence Intervals for the means or the percentages will be produced if appropriate to explain the results [1].

Table will display data for each treatment group and overall (=Total column).

All data recorded in the CRF will be listed and sorted by treatment groups, subject number and visits [See Appendix 1].

Considering that the study is designed as phase I/II, in which phase I concerns to the primary endpoint (Safety) and phase II concerns to the preliminary data on effectiveness of sFilm-FS, data will not be presented in the two distinct frames, phase I and phase II.

The probability level for all analyses will be set at 5% and appropriate 95% Confidence Intervals will be produced according to the nature of the variables and will be based on a valid case approach, if so [e.g. percentages will be based on the number of observations available at the specific time point and not based on the number of patients at the visit.

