6.12 Safety Evaluation

As previously stated, Safety is the primary endpoint.

Safety could be a composite endpoint because include more than one variable:

- ✓ Adverse Events
- ✓ Thrombotic Events
- ✓ Transfusion-Related Complications
- ✓ MRI Assessment (post-operative adhesions)
- ✓ Signs of Systemic Inflammations
- ✓ Antibodies against Fibrinogen and Thrombin
- ✓ Physical Examination
- ✓ Vital Signs
- ✓ Blood and Coagulation Parameters
- ✓ Urine Analyses

All Safety data will be listed by patients and treatment groups at each collected time and tabulated with the appropriate descriptive statistics by treatment groups at each collected

	STATISTICAL ANALYSIS PLAN	FSTAT.01.03
Study Code: HEM-HEM-01-17		Sealantium Medical Ltd.

time.

Considering that no hypothesis testing for difference between treatments groups concerning AEs related to bleeding at TBS and the other safety data was planned in the protocol, only 95% confidence limits on differences between treatments will be done.

Concerning safety data, an independent data review will be done by a medical reviewer before data review meeting and database lock. The medical reviewer will identify and classify all safety endpoints with respect to e.g. thrombotic events, transfusion complications, etc. and will check correctness of MeDDRA classification (PT, SOC). At the end of this review, medical reviewer will be produced a detailed report.

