6.12.6.2 Biochemistry

Biochemistry data will be recorded at Screening, Baseline, Surgery, Hospital Discharge and Follow-up ((after 30, 60, 120 and 180 days from Surgery): Blood Urea Nitrogen (BUN), Creatinine, Glucose, Lactate Dehydrogenase (LDH), Total Proteins, Albumin, Total Bilirubin, Uric acid, Aspartate Transaminase (AST), Alanine Amino Transferase (ALT), Gamma Glutamyl Transferase (GGT), D-Dimer, C-Reactive Protein (CRP), Anti-thrombin and Lactate, Sodium, Calcium, Phosphorus.

Summary statistics as denoted under 2.-4. will be presented.

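### The SAP promises between-arm 95% limits for laboratory safety values but gives no scale or valid method for continuous ones, and plans no baseline adjustment or log scale

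*SAP*

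**What the plan says.** SAP 3.3.1 and 6.12 make blood and coagulation parameters part of the primary (safety) endpoint. No test is planned: Protocol 14.5 states "Hypothesis testing is not specified for this study". For adverse events and the other safety data, SAP 6.12 therefore says that "only 95% confidence limits on differences between treatments will be done".

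For laboratory data, SAP 6.12.6 numbers five outputs:

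1. counts for categorised parameters;
2. descriptive statistics by time point for continuous ones;
3. counts of normal, abnormal not clinically significant and abnormal clinically significant values;
4. shift tables against baseline;
5. "All continuous parameters will show tables with absolute change from Baseline".

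The hematology, biochemistry and coagulation subsections (6.12.6.1 to 6.12.6.3) call items 2-4, and urine (6.12.6.4) calls items 1-4. None calls item 5.

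SAP 6.1 summarises continuous data by mean, SD, standard error, median and range. The one interval method it names, for means as well as percentages, is Clopper-Pearson.

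The biochemistry list includes "D-Dimer, C-Reactive Protein (CRP), Anti-thrombin and Lactate, Sodium, Calcium, Phosphorus". A pre-operative value is available: Protocol 11.1.1 collects it at screening, and Protocol 11.1.2 schedules "Blood hematology and biochemistry (see Schedule of Assessments for the list of tests" again on the day before surgery. SAP 6.8 defines baseline as the value shortly before product application. On sample size, Protocol 14.1 says "The sample size of 15 patients per arm is sufficient for planned descriptive analyses".

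**The concern.** Interval estimates are the only between-arm comparison planned for these components of the primary endpoint. For a continuous laboratory value the reader cannot tell what will be differenced (follow-up value, change or something else), on which scale, or by which formula. The one method named for means does not produce an interval for a mean.

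The choice matters with 15 patients per arm. Markers such as AST, ALT, LDH, bilirubin, CRP and D-dimer can be expected to be right-skewed after liver surgery. That is an assumption, since the documents give no distributions. One or two extreme values can then dominate an arithmetic mean and widen its limits. The baseline value can also remove between-patient variation at no cost in data collection. The only covariate adjustment mentioned (Protocol 14.7.2) is optional and concerns efficacy. Leaving scale and model open in an open-label trial also leaves them to be chosen after the data are seen.

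**Working it through.** **1. The plan's own precision figure.** Protocol 14.8.2 gives 52% to 96% for 80% hemostasis in 15 patients. Clopper-Pearson for 12/15: lower limit = Beta(12, 4) quantile at 0.025 = 51.9%; upper limit = Beta(13, 3) quantile at 0.975 = 95.7%. The figure reproduces. It is the only precision figure in the documents, and none is given for any laboratory value.

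**2. Inputs.** From the documents: 15 per arm and 95% limits. Assumed, because the documents give none: baseline correlation ρ, spread, skewness, and equal spread at baseline and follow-up.

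**3. Nearly symmetric marker, SD = 1 at both times.** Half-width of the 95% limits:

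- raw follow-up: t(28 df) × √(2/15) = 2.048 × 0.365 = 0.748
- change: 0.748 × √(2(1−ρ))
- baseline-adjusted: t(27 df) × √(2/15) × √(1−ρ²) × √(1+1/26), where the last term is the average cost of estimating the slope

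| ρ | raw | change | baseline-adjusted |
|---|---|---|---|
| 0.2 | 0.748 | 0.946 | 0.748 |
| 0.5 | 0.748 | 0.748 | 0.661 |
| 0.7 | 0.748 | 0.579 | 0.545 |
| 0.8 | 0.748 | 0.473 | 0.458 |

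Against the better of raw and change, adjustment narrows the limits by at most about 12% (ρ = 0.5: 0.661/0.748 = 0.88). Against the worse of the two it gains more: 0.946 to 0.748 at ρ = 0.2, and 0.748 to 0.458 at ρ = 0.8.

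**4. Skewed marker.** Simulation of 15 v 15 patients with log-normal baseline and follow-up, equal log SD at both times and a true two-fold difference. Share of trials whose 95% limits exclude no difference:

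| log SD | ρ | raw follow-up | absolute change | log scale with baseline |
|---|---|---|---|---|
| 0.9 | 0.3 | 40% | 33% | 55% |
| 0.9 | 0.6 | 40% | 50% | 71% |
| 0.6 | 0.3 | 80% | 74% | 88% |
| 0.6 | 0.6 | 80% | 91% | 96% |

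Repeat runs move these figures by a point or two. At log SD 0.3 every method excludes no difference in practically every run, so a two-fold difference shows no loss there. With no true difference, log-scale limits exclude it in about 5% of runs. Raw-scale limits do so in about 4% at log SD 0.9, so they are slightly conservative.

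**5. Which change does the work (log SD 0.9).** The log scale without baseline gives 53% at either correlation. At ρ = 0.3 the steps are raw 40%, log 53%, log with baseline 55%, so nearly all the gain comes from the scale. At ρ = 0.6, adding baseline moves 53% to 71%.

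**6. Number of intervals.** SAP 6.12.6.1 to 6.12.6.3 list 10 hematology, 18 biochemistry and 3 coagulation parameters. The SAP gives six post-baseline time points for the first two groups and four for coagulation: 28 × 6 + 3 × 4 = 180 intervals. With no true difference anywhere, about 0.05 × 180 = 9 would exclude it by chance.

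**The case against.** The strongest reply has four parts.

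- **The SAP does not say that the limits rest on raw values or absolute change.** A reader might infer this by joining SAP 6.12 (limits) to 6.12.6 (tables), but item 5 describes tables and no laboratory subsection calls it. This stands. The documented defect is that scale and method are missing, not that poor ones were chosen.
- **The gain depends on unknown inputs.** This stands too. The familiar rule that a change score is less precise than the follow-up value below a correlation of 0.5 needs equal SDs at both times. If the baseline SD is 0.3 of the follow-up SD and ρ = 0.3, the relative standard error of change is √(1 + 0.09 − 0.18) = 0.954, and baseline adjustment gives √(1 − 0.09) = 0.954, which is no gain. At very high correlation, adjustment adds almost nothing over change.
- **Other output protects against missed signals.** Medians, ranges, flags, clinical-significance counts, shift tables and an independent medical review are all planned. They help, and the shift tables do use baseline in categories. None of them gives a between-arm limit for a continuous value, which is what SAP 6.12 promises.
- **Counting exclusions of zero is test logic in an exploratory study with about 180 intervals.** This is fair as to wording: the percentages here are a gauge of precision. The multiplicity point applies equally to the limits already promised, whatever the model.

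**Conclusion.** The point holds as a specification gap with a modest, marker-dependent cost. SAP 6.12 commits to limits that 6.1 and 6.12.6 give no usable way to compute for continuous values, item 5 conflicts with the subsections, and neither baseline adjustment nor a log scale is planned.

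Under the stated assumptions, a strongly skewed marker (log SD 0.9) gains 15 points over raw follow-up and 22 over change at correlation 0.3, and 31 and 21 points at 0.6. At log SD 0.6 the gains are 8 and 14 points, then 16 and 5. For nearly symmetric markers the limits narrow by at most about 12% against the better simple option.

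A reader might go further and conclude that real laboratory shifts will be missed. The documents do not support that: no test is planned, other safety output is extensive, and correlation and skewness are unknown. The consequence is wider limits than necessary and a method left open. This is an inexpensive improvement, not a threat to the trial.

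**What to change.** Add to SAP 6.12.6: between-arm 95% limits for continuous laboratory and coagulation parameters at each post-baseline time point come from a linear model with treatment and baseline value. A prespecified list of right-skewed markers (for example AST, ALT, GGT, LDH, bilirubin, CRP, D-dimer and lactate) is analysed on the log scale and reported as ratios of geometric means.

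In addition:

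- in SAP 6.1, limit Clopper-Pearson to single-arm proportions;
- keep the raw, change and shift tables as descriptive output;
- reconcile item 5 with the references to items 2-4 and 1-4 in 6.12.6.1 to 6.12.6.4;
- state that the many laboratory intervals are exploratory and not adjusted for multiplicity, in line with SAP 6.6.

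The cost is SAP wording and routine programming. The baseline values are already collected. The one drawback is that some results become ratios and not absolute differences, which the retained descriptive tables offset.
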